Title: Does early platelet rich plasma injection decrease the risk of post-traumatic arthritis in pilon fractures undergoing two-staged open reduction with internal fixation?

Protocol version: 1.3

Protocol date: 08/30/2016

Principal Investigator: [name]

NCT: 02481869

A) Scientific Aims

Specific Aim 1: Determine the effects of a single intra-articular injection of platelet rich plasma (PRP) for mitigating the development of post-traumatic arthritis (PTA) in patients being surgically treated for pilon fractures in one ankle.

Null hypothesis: A single intra-articular injection of platelet rich plasma (PRP) will not be associated with significant improvements in outcome based on patient-reported measures of pain and function, as well as diagnostic imaging findings of PTA in patients being surgically treated for pilon fractures in one ankle.

Specific Aim 2: Assess the discriminatory potential of a synovial fluid biomarker panel for categorizing presence and severity of PTA based on patient-reported outcome measures of pain and function, as well as diagnostic imaging findings in patients being treated for pilon fractures in one ankle.

Null hypothesis: Synovial fluid biomarkers will not have high discriminatory capabilities for categorizing presence and severity of PTA in patients being treated for pilon fractures in one ankle.

B) Background and Significance

Pilon fractures are common and are associated with a 75% chance for symptomatic post-traumatic arthritis (PTA).¹ Although the mechanisms for initiation and progression of PTA after pilon fracture are incompletely understood, articular fracture is known to induce pro-inflammatory cytokines and degradative enzymes, which can result in chondrocyte death, accelerate cartilage degradation, and drive synovitis after injury. These pathologic processes appear to be especially important in the early phases of disease.²⁻⁴ Current treatments for articular fractures are focused on biomechanical issues: anatomic reduction, rigid stability, and limb alignment. These are critical issues to address for optimal healing, early limb use, and joint function. However, the biologic components of articular fracture are likely as, or even more important, with respect to development of PTA. As such, research efforts also need to focus on these important aspects in order to mitigate the development and progression of joint pathology after articular fracture.

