In an in vitro study, antioxidant treatment delivered hours after articular cartilage injury was reported to prevent progression of PTA-related pathology.⁵ Using canine models of PTA, our group has noted significant benefits after intra-articular injection of platelet rich plasma (PRP) in decreasing pain, improving limb use, maintaining joint range of motion, and mitigating progression of osteoarthritis. Beneficial results associated with PRP treatment of OA have also been reported in clinical veterinary patients.⁶ Based on this translational evidence in conjunction with the regulatory status and availability of PRP for clinical use in trauma patients, this orthobiologic therapy appears to have strong potential for providing a practical means of mitigating development of PTA in patients suffering ankle fracture. Importantly, we will be able to use a synovial fluid biomarker panel that has been shown to have high discriminatory potential for categorizing presence and severity of OA in dogs⁹, to assess patients for PTA after pilon fracture – which provides critical data regarding disease mechanisms^{7,8} – and treatment monitoring for development and assessment for novel therapeutic strategies for this pervasive problem.

C) Previous Work on the Study

There has been little published work on this particular treatment strategy for post traumatic arthritis of the ankle

D) Methods

With IRB approval and informed consent, patients (n=40) will be included who sustain closed pilon fracture of one ankle and are undergoing initial reduction with spanning external fixation, followed by open reduction with internal fixation (ORIF). Up to 50 patients will be enrolled in order to account for expected attrition in this patient population. Patients will be randomized to one of two treatment groups:

- PRP (n=20): single intra-articular injection of 5 ml of a leukocyte-reduced platelet rich plasma (ACP, Arthrex, Naples, FL) at the time of closed reduction and initial stabilization using ankle-spanning external fixation

- Control (n=20): single intra-articular injection of 5 ml of sterile 0.9% saline at the time of closed reduction and initial stabilization using ankle-spanning external fixation

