## **Sample Size Determination**

Number of patients per group was determined from a pre-study power analysis using previously published data on prevalence of PTA after pilon fracture – the assumption being that a 10% reduction in percentage of patients experiencing symptomatic PTA would be clinically significant.

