## **Data Analysis**

For data analysis, PTA presence will be defined based on a diagnosis of OA, or findings consistent with OA, reported for either imaging modality at any assessment time point. PTA severity will be determined from whole-joint MRI scoring and patient reported outcomes at 18 months after surgery and categorized as mild, moderate or severe. To test the first hypothesis, we will compare treatment groups for statistically significant ( $p < 0.05$ ) differences in proportions with PTA, proportions within each severity category, and PRO scores using Fisher's exact tests, t-Tests, and rank sum tests. To test the second hypothesis, we will perform receiver operator characteristic curve analyses to determine the discriminatory capabilities (area under the curve (AUC)) of the panel for distinguishing the presence and severity of PTA. The injured ankle will be compared to the normal, contralateral ankle and  $AUC > 0.8$  will be considered to represent high and clinically useful discriminatory capability. In addition, patient age, gender, BMI, tobacco use, and co-morbidities, as well as the pre-operative CT scan injury severity score will be assessed as variables for predicting likelihood of presence and severity of PTA using Fisher's exact test and odd's ratios.

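### AUC > 0.8 alone is allowed to earn the label 'clinically useful', with no cut-off, predictive values or decision context to support it

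*SAP*

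**What the plan says.** The SAP, Data Analysis, plans ROC analyses to find the AUC "of the panel for distinguishing the presence and severity of PTA". The next sentence names a comparison, "The injured ankle will be compared to the normal, contralateral ankle", and sets the criterion: an AUC above 0.8 "will be considered to represent high and clinically useful discriminatory capability". Protocol section D has the same text.

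PTA presence for the analysis is an imaging outcome: an OA diagnosis, or findings consistent with it, on either modality at any assessment. No expected rate is given for it. The only PTA rate in the documents is in Protocol section B, where pilon fractures are "associated with a 75% chance for symptomatic post-traumatic arthritis".

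Neither document names a cut-off, a sensitivity or specificity target, a predictive value, or a clinical decision that the panel result would serve.

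**The concern.** The criterion joins two claims. 'High' discrimination is a statement about ranking, and an AUC threshold is a normal way to define it. 'Clinically useful' is a statement about what a result tells a clinician about a patient. That depends on the cut-off and on how common PTA is, and AUC fixes neither. The gap remains even if the true AUC were known exactly.

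What is at stake is the wording of the Aim 2 conclusion. Followed as written, an AUC just above 0.8 would be reported as clinically useful with no predictive values beside it. The reader could not tell whether a positive or a negative panel result adds much to what is already known about a population in which PTA is common.

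**Working it through.** The documents give no derivation of the 0.8 threshold, so there is no figure to reproduce. The check asks what a panel that only just meets it could deliver.

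**Inputs from the documents**
- AUC = 0.80, the boundary of the criterion (SAP, Data Analysis).
- PTA rate π = 0.75 (Protocol B, symptomatic PTA).
- 40 patients (Protocol D), so 30 with PTA at that rate.

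**Assumptions, not in the documents**
- Equal-variance binormal scores.
- A PTA v no-PTA contrast among injured ankles.
- The cut-offs shown.

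**Formulas**
- Separation d = √2 × Φ⁻¹(0.80) = 1.19.
- Balanced cut-off: Se = Sp = Φ(d/2) = 0.724.
- Accuracy-maximising cut-off, with the threshold measured from the no-PTA mean: d/2 + ln[(1−π)/π]/d = 0.595 − 1.099/1.190 = −0.328. This gives Sp = Φ(−0.328) = 0.3715 and Se = Φ(1.190 + 0.328) = 0.9355.
- PTA among test-negatives (1 − NPV) = π(1−Se) / [π(1−Se) + (1−π)Sp].
- PPV = πSe / [πSe + (1−π)(1−Sp)].
- Accuracy = πSe + (1−π)Sp. Calling every patient PTA has accuracy π.

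**Balanced cut-off, π = 0.75**
- 1 − NPV = 0.207 / (0.207 + 0.181) = 53%.
- PPV = 0.543 / (0.543 + 0.069) = 89%.
- Accuracy = 72.4%, against 75%.
- In 40 patients: about 15.5 test negative, of whom 8.3 have PTA.

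**Accuracy-maximising cut-off, π = 0.75**
- 1 − NPV = 0.0484 / (0.0484 + 0.0929) = 34%.
- PPV = 0.7016 / (0.7016 + 0.1571) = 82%.
- Accuracy = 0.7016 + 0.0929 = 79.5%, a gain of 4.5 points.

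**Across cut-offs, π = 0.75**

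| Se | Sp | PTA among test-negatives | Accuracy (75% if all called PTA) |
|---|---|---|---|
| 0.724 | 0.724 | 53% | 72.4% |
| 0.80 | 0.64 | 48.5% | 75.9% |
| 0.90 | 0.46 | 39% | 79.1% |
| 0.936 | 0.371 | 34% | 79.5% |

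**Other PTA rates, equal variances**

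If the 10% reduction in SAP, Sample Size Determination, is absolute, the arms would be at 75% and 65%, pooled 70%.

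| PTA rate | PTA among test-negatives, balanced cut-off | Best accuracy | All called PTA | Gain |
|---|---|---|---|---|
| 75% | 53% | 79.5% | 75% | 4.5 points |
| 70% | 47% | 76.9% | 70% | 6.9 points |
| 65% | 41% | 74.9% | 65% | 9.9 points |

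**ROC shape, π = 0.75**

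With the PTA to no-PTA SD ratio varied from 0.7 to 1.4, PTA among test-negatives is 45% to 56% at the cut-off maximising Se + Sp, and 23% to 45% at the best-accuracy cut-off. Best accuracy runs from 82.5% down to 76.6%.

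**Comparator**

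If the 40 contralateral ankles are pooled in as negatives, PTA is 30/80 = 37.5% and the balanced-cut-off figure falls to 19%. The same AUC of 0.80 then carries very different predictive values.

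**The case against.** A reader might infer that a panel at AUC 0.80 leaves about half of test-negative patients with PTA and barely beats calling everyone positive. The documents do not support that as a property of the threshold, for four reasons.

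- The two halves belong to different cut-offs. At the balanced cut-off about half of test-negatives have PTA, but accuracy is below the benchmark. At the best-accuracy cut-off there is a gain, but about a third of test-negatives have PTA. The halves coincide only near a sensitivity of 0.80.
- The 75% is a background rate for symptomatic PTA. The analysed outcome is defined by imaging, and its rate is not given. At lower rates the accuracy gain grows.
- Raw accuracy is a harsh yardstick for a cut-off that weights sensitivity and specificity equally, and rule-in value remains: PPV is 89% against a 75% base rate. The documents do not propose the panel as a rule-out test.
- The AUC sentence itself refers to injured v contralateral ankles, so it is unclear that the AUC will measure PTA v no PTA among patients. That ambiguity is arguably the larger problem.

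It can also be said that the Aim 2 null hypothesis speaks only of high discriminatory capability, so deleting 'clinically useful' would not change the test decision.

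All of this stands against the stronger reading. None of it supplies a basis for the label: the plan still names no cut-off, predictive value or decision. That results swing so widely with cut-off, PTA rate and comparator is itself the reason AUC alone cannot carry the claim.

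**Conclusion.** The point holds in limited form. An AUC above 0.8 can define high discrimination, but it neither guarantees nor excludes clinical usefulness, and the plan offers nothing else to support that term.

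The size depends on the assumptions set out in the working, chiefly the 75% rate borrowed from symptomatic PTA and the equal-variance ROC. Under them, a panel just at the threshold spans results from worse than calling every patient PTA to modestly better, and a negative result leaves between a third and a half of patients with PTA. These figures illustrate the gap and do not predict what the panel will do. They do not show that the panel would be useless.

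The consequence is confined to what Aim 2 may conclude. The treatment comparison is untouched.

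**What to change.** In SAP Data Analysis and Protocol section D:

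1. Keep AUC > 0.8 as the mark of 'high' discrimination and delete 'and clinically useful'.
2. State that the ROC for PTA presence contrasts PTA with no PTA among injured ankles.
3. Fix one cut-off rule for that ROC before outcomes are joined to the marker data, for example the cut-off giving 90% sensitivity.
4. At that cut-off, report sensitivity, specificity, PPV and NPV with exact 95% intervals at the observed PTA rate. Show the observed PTA rate beside them as the benchmark for calling every patient PTA.
5. Limit the Aim 2 conclusion to discrimination.

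The cost is a wording change in two documents and a few statistics from data already planned. The downside is a less favourable claim and imprecise predictive values: with 15 test-negative patients, an NPV of 7/15 = 47% has an exact 95% interval of 21% to 73%.

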Study candidates will be identified as they present to the University Hospital emergency room or clinics and will be recruited for enrollment. Informed consent will be obtained as per IRB protocol. The patients will be approached by an orthopedic resident physicians, attending, or study staff to present the current study. Patients will be told of the details of the study and what is required of them if they chose to participate. The patients will be randomized by envelope to one of two groups, the PRP or control group. The patients will be blinded to which treatment they receive. Patients will be treated according to current standard of care, Following initial reduction and placement of ankle-spanning external fixation, synovial fluid will be aseptically obtained via arthrocentesis from both ankles and saved for subsequent biomarker analysis at the Comparative Orthopedic Laboratory. For the injured ankle, the PRP injection will be performed through the same needle used for arthrocentesis. PRP will be isolated from venous blood drawn from a peripheral vein. When appropriate, ORIF will be performed for definitive fracture treatment likely 7-14 days following external fixator placement. Prior to capsulotomy for ORIF, synovial fluid will again be aseptically obtained via arthrocentesis from both ankles and saved for subsequent biomarker analysis.

Follow-up assessments will be performed at 3 weeks, 6 weeks, 12 weeks, 6 months, 12 months, and 18 months after surgery for all patients. Radiographs will be obtained at 6 weeks and each subsequent visit. Patient reported outcomes (PRO) including AOFAS, SF 12 and VAS for pain and level of function will be recorded at all follow-up assessments starting at 3 weeks. At 18 months, MRI of the affected ankle will be performed and used for whole-joint assessment of OA.¹⁰

Number of patients per group was determined from a pre-study power analysis using previously published data on prevalence of PTA after pilon fracture – the assumption being that a 10% reduction in percentage of patients experiencing symptomatic PTA would be clinically significant. Patients and all patient evaluators will be kept blinded to treatment until all data are collected and analyzed by the co-investigator responsible for

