all data analyses. For data analysis, PTA presence will be defined based on a diagnosis of OA, or findings consistent with OA, reported for either imaging modality at any assessment time point. PTA severity will be determined from whole-joint MRI scoring and patient reported outcomes at 18 months after surgery and categorized as mild, moderate or severe. To test the first hypothesis, we will compare treatment groups for statistically significant ($p < 0.05$) differences in proportions with PTA, proportions within each severity category, and PRO scores using Fisher's exact tests, t-Tests, and rank sum tests. To test the second hypothesis, we will perform receiver operator characteristic curve analyses to determine the discriminatory capabilities (area under the curve (AUC)) of the panel for distinguishing the presence and severity of PTA. The injured ankle will be compared to the normal, contralateral ankle and $AUC > 0.8$ will be considered to represent high and clinically useful discriminatory capability. In addition, patient age, gender, BMI, tobacco use, and co-morbidities, as well as the CT scan injury severity score¹¹ will be assessed as variables for predicting likelihood of presence and severity of PTA using Fisher's exact test and odd's ratios.

Based on its mechanisms of action and preliminary data, we expect to reject our null hypotheses and show that a single injection of PRP is associated with significant improvements in outcomes. We also expect that our synovial fluid OA biomarker panel will have high discriminatory capabilities for categorizing presence and severity of PTA in patients being treated for pilon fractures in one ankle.

Subject Selection

Inclusion criteria:

- Patients with closed unilateral pilon fractures
- Patients undergoing staged pilon procedures with an external fixator index procedure

Exclusion criteria:

- Patients who are younger than 18 years of age
- Open pilon fracture
- Patients with contralateral lower extremity injury
- Patients unable to comply with the follow-up appointments
- Patients who had previous ankle injury to the currently injured ankle
- Patients who are pregnant
- Prisoners

E) Re-consent of previously incompetent subjects

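### Age, BMI and the CT score are assessed as predictors of PTA with Fisher's exact test and no cut-points; keeping them continuous removes that choice and usually gives clearly more power

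*SAP*

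**What the plan says.** The predictor analysis is the last sentence of the SAP's Data Analysis section. It names "patient age, gender, BMI, tobacco use, and co-morbidities, as well as the pre-operative CT scan injury severity score" and says that these "will be assessed as variables for predicting likelihood of presence and severity of PTA using Fisher's exact test and odd's ratios". Protocol section D) Methods has the same list, "patient age, gender, BMI, tobacco use, and co-morbidities, as well as the CT scan injury severity score", with the same method.

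Neither document gives a cut-point, a grouping rule or a regression model for age, BMI or the CT score. Neither says whether the CT score is numeric or graded. The t-tests and rank sum tests in the same SAP section belong to the comparison of treatment groups ("proportions within each severity category, and PRO scores using Fisher's exact tests, t-Tests, and rank sum tests"), so they do not supply a method for the predictors.

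PTA presence is a yes/no outcome taken from imaging: "PTA presence will be defined based on a diagnosis of OA, or findings consistent with OA, reported for either imaging modality". Severity has three ordered levels.

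**The concern.** Fisher's exact test works on a table of counts. Age and BMI are measured on a scale and must be grouped before the test can be run, and the same is true of the CT score if it is numeric. Because no grouping is stated, two analysts could both follow the plan and report different predictors of PTA.

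Two things are at stake:
- **Power.** Grouping discards information in a trial of 40 patients, of whom perhaps 10 will be free of PTA.
- **Error rate.** If the cut is chosen after the outcomes are known, the false-positive rate rises.

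**Working it through.** **Inputs from the documents.** N = 40, 20 per group (Protocol, D) Methods). The PTA rate comes from Protocol, B) Background and Significance, which says pilon fractures "are associated with a 75% chance for symptomatic post-traumatic arthritis". That figure is for symptomatic PTA; I assume that it carries over to the imaging definition. The expected number free of PTA is then 40 × 0.25 = 10. The plan states no power or sample size for the predictor analysis, so there is no figure to reproduce.

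**Assumptions.** The predictor is normal, and its mean is lower by d standard deviations in PTA-free patients. Tests are two-sided at p<0.05. Cuts leave 10, 13, 20, 27 or 30 of the 40 patients below (roughly the 25th, 33rd, 50th, 67th and 75th percentiles).

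**Formula.** With f PTA-free patients among 40 and m patients below the cut, the chance that k of the f fall below is C(f,k) × C(40−f, m−k) / C(40, m). Fisher's p-value sums this over all tables no more likely than the one observed.

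**Main result.** Simulation, with the number of PTA-free patients varying as binomial (40, 25%):

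| | Fisher, five cuts in order | t-test, uncut | Cuts disagree at p<0.05 |
|---|---|---|---|
| d = 1 | 46%, 49%, 41%, 29%, 23% | 75% | 63% |
| d = 0.5 | 8% to 14% | 26% | 29% |

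With d = 0, a fixed cut rejects about 3% of the time and the best of the five about 9%. In a separate run, the best of all cuts between the 20th and 80th percentiles rejected about 20%.

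**Why the PTA-free number must vary.** With exactly 10 PTA-free patients the Fisher powers at d = 1 are 38%, 38%, 29%, 31% and 49%, which makes the highest cut look best. That is an artefact of discreteness. None of 10 PTA-free patients above a cut with 10 patients above has probability C(30,10)/C(40,10) = 0.035, and p = 0.043 once the other tail is added. With 9 PTA-free patients the same pattern gives p = 0.081, so power at that cut is 0%. Averaged over the likely numbers, the highest cut is the worst. If PTA-free patients had the higher values instead, the order of the cuts would reverse.

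**Other PTA rates, d = 1.**
- 26 with PTA and 14 without: Fisher 28% to 61%, t-test 83%.
- 36 with PTA and 4 without: a median split cannot reach p<0.05. Its most extreme table has p = 2 × C(20,4)/C(40,4) = 2 × 4845/91390 = 0.106. All 4 in a group of 10 gives C(10,4)/C(40,4) = 210/91390 = 0.002. Power is 45% at the 25th percentile, 19% at the 33rd and 0% at the other three cuts, against 46% for the t-test.

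**A different model.** Here PTA follows a logistic curve in the predictor, with N = 40 and 75% PTA. The continuous range covers likelihood-ratio, Wald, rank sum and t-tests.
- Odds ratio 2 per SD: median-split Fisher 19%, continuous 36% to 43%.
- Odds ratio 3 per SD: 41%, against 69% to 77%.
- True step in risk at the median, odds ratio 9: 51%, against 48% to 58%, so about equal.
- Skewed predictor, odds ratio 2: Fisher 13%, likelihood-ratio 32%, rank sum 24%, t-test 18%, Wald 12%.

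**The proposed model.** Firth logistic regression with a penalised likelihood-ratio test (treatment group included, exactly 30 vs 10) rejects 4.6% with no association, 25% at d = 0.5 and 73% at d = 1.

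**The case against.** Four objections have weight.

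- **The scenario suits the continuous test.** A normal predictor with a mean shift is the t-test's ideal case. This stands in part: with a step in risk at the cut the methods are level, and with a skewed predictor a Wald test gains nothing. One well-placed cut can also match the t-test when few patients are PTA-free. The advantage is therefore usual, not universal, and the sponsor cannot know the favourable cut in advance.
- **Part of the gap is Fisher's conservatism.** True: a fixed cut rejects about 3% under no association, against a nominal 5%. The simulations do not separate this from the information lost by cutting.
- **No significance threshold is set for the predictors.** True: p<0.05 is attached only to the treatment comparison, so the disagreement figures rest on an assumed rule. The odds ratio would still depend on an unstated cut.
- **An odds ratio can come from a logistic model.** It can, but no such model is named, and the test that is named needs groups.

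A reader might also infer that the PRP comparison is faulty because it is not adjusted for the CT score. The documents do not support that. The unadjusted comparison of randomised groups is valid. Any gain in precision depends on a correlation between CT score and PRO that is not given, and on a score whose scale is not stated and whose date relative to the injection is not confirmed. Nor is the listing of three tests together a defect of the same kind: it reads naturally as Fisher's test for proportions and t or rank sum tests for scores.

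**Conclusion.** The point holds as a minor one. The plan assigns a test for categories to variables measured on a scale, with no cut-point. Under the stated assumptions, at a 1 SD difference most of the cuts examined leave less than two-thirds of the power of the uncut values (49/75 = 65% at best, 23/75 = 31% at worst), and the choice of cut often decides the result.

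The figures rest on 75% symptomatic PTA applying to the imaging definition, a normal predictor, assumed differences of 1 and 0.5 SD, and two-sided testing at p<0.05. Only PTA presence was simulated, not severity.

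A reader might take this to weaken the trial's main findings. It does not: the SAP introduces the analysis as an addition to the two hypothesis tests, and the PRP and biomarker conclusions do not depend on it. Nor do the documents say that cuts will be chosen after seeing the outcomes; they only leave that open.

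**What to change.** Amend the SAP's Data Analysis section, and Protocol D) Methods to match:

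- Analyse age, BMI and, if numeric, the CT score as continuous predictors, one at a time. With about 10 PTA-free patients a joint model of all of them would not be reliable.
- For PTA presence, use penalised (Firth) logistic regression with a likelihood-ratio test. For severity, use an ordinal model.
- Report odds ratios with 95% confidence intervals per stated unit of each variable.
- Keep Fisher's exact test for the categorical factors.
- If a cut-point is kept for any variable, state it before outcome data are seen.

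The cost is a few sentences of SAP text and a check of the CT score's scale; no new data are needed. The downside is an assumption of linearity on the log-odds scale and, for severity, of proportional odds.
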